Identifying factors that can potentially interrupt this cycle has significant implications for public health. Growing evidence indicates that DHA supplementation improves maternal stress reactivity during pregnancy and protects neurodevelopment of the offspring, especially in the context of high levels of stress exposure. We propose a program of research that aims to translate such findings to address the significant health disparities for African American women and children. In the following section we present preliminary evidence for the efficacy of prenatal fatty acid supplementation on maternal perceived stress and stress reactivity in this high-risk population.

Preliminary support for hypotheses

We recently completed the first randomized controlled trial of DHA supplementation among pregnant African American women living in stressful, low-income, urban environments (for a full report see Keenan et al., in press, *Obstetrics & Gynecology*). Sixty-four pregnant women were recruited from the Obstetrics Clinics at the University of Pittsburgh. Inclusion criteria were: African American race, age between 20 and 30 years, 16-21 weeks of gestation, Medicaid insurance or Medicaid eligible, and low levels of DHA consumption as defined as less than two fish servings per week. Exclusion criteria were medical complications (e.g., gestational diabetes, pre-eclampsia), regular use of steroid medications, use of blood thinners or anti-coagulants, use of psychotropic medications, current BMI >40, and allergy to iodine and/or soy. Participants were reimbursed on an accelerated schedule with \$40 for their first visit and an increase in payments of \$10 for each subsequent visit. The Institutional Review Boards of the Universities of Chicago and Pittsburgh approved all study procedures. Once enrolled, women were randomly assigned to receive the omega-3 nutritional supplement (n = 43) or a corn and soybean oil placebo (n = 21) beginning at enrollment and up through the end of pregnancy. Women received supplement via two gel capsules providing: 450 mg of DHA; 40 mg of docospentaenoic acid (DPA) and eicosatetranoic acid

[figure not shown]
(ETA); 90 mg of eicosapentaenoic acid (EPA); and 15 IU of Vitamin E. Randomization was conducted by the pharmacy at the University of Pittsburgh, thus ensuring that participants and investigators were blinded to the group to which the participants were assigned.

[figure not shown]

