In addition to associations between DHA supplementation and prenatal stress, we observed significantly higher birth weights among neonates born to women receiving DHA compared to placebo controlling for gestational age (3,174 grams versus 2,889 grams, p = .018) and greater likelihood of having a 1-minute Apgar score of 9 (odds ratio = 5.99 [95% Cl = 1.25 - 28.75], p = .025, controlling for birth weight and gestational age). Finally, 13% of neonates of mother receiving DHA supplementation were born prior to 37 weeks, compared to 22% of mothers received placebo; a difference that did not reach the level of statistical significance in the pilot study, but is clinically meaningful.

In summary, the data from our preliminary study are compelling in terms of the potential impact on health disparities in maternal and infant health, a significant public health problem that is poorly understood. We now seek to expand on these preliminary findings by conducting a more rigorous assessment of prenatal DHA supplementation on maternal and infant health by increasing the number of participants to 162, beginning supplementation earlier in pregnancy, adding additional measures of maternal health and stress response during pregnancy, increasing the frequency of assessment, assessing DHA levels in red blood cells at each visit, and including multiple postnatal assessments of infant neurodevelopment. The proposed study offers an opportunity for replication and to test the impact of supplementation on infant functioning and, if effects are observed, whether they are mediated by changes in prenatal stress.

APPROACH

Participants

One hundred-sixty-eight pregnant, African American, women will be recruited from the University of Chicago obstetric clinic. Inclusion criteria will include: age between 18 and 34 years, household receipt of public assistance (e.g., Medicaid insurance) due to low-income, and low levels of DHA consumption as defined as less than two fish servings per week. Exclusion criteria are reports of known medical complications, regular use of steroid medications, alcohol, cigarettes, or illegal substances (by maternal report), use of blood thinners or anti-coagulants, use of psychotropic medications, BMI >40, and allergy to iodine and/or soy. Participants may be excluded if medical complications arise after enrollment. Neonates with significant medical complications will be maintained in the study.

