There are two reasons for our focus on African American women. First, as described above, African American women are disproportionately represented among families living in inner-city poverty and have the highest rates of suboptimal birth outcomes in the U.S. (Giscombé & Lobel, 2005). Second, there are racial differences in cortisol reactivity to

stress and pregnancy (De Santis et al., 2007; Glynn et al., 2007; Wilcox et al., 2005) and in the genes regulating cortisol (Baerwald et al., 1999). Given the scope of the proposed study and the potential to generate data that can be translated into reductions in health disparities, we chose to study African Americans only, but acknowledge that it will be important to test racial and ethnic differences in maternal and infant response to DHA supplementation during pregnancy.

Women will be randomly assigned to receive the omega-3 nutritional supplement (n = 112) or a corn and soybean oil placebo (n = 56) beginning at enrollment and up through the end of pregnancy. In the proposed design we allocate the number of participants to groups to optimize power to test the hypotheses. We expect greater variability in the independent measure (i.e. DHA level) and dependent measures (e.g., stress reactivity) in participants in the experimental group than those in the control group given anticipated differences in uptake and metabolism. Thus, we plan to enroll a higher number of participants in the experimental group than in the control group to adequately capture that variability (Cox, 1958). Participants and investigators will be blinded to the group to which they have been assigned. Treating clinicians will identify demographically eligible participants who will be contacted by research staff for further screening. Participants who meet the inclusion and exclusion criteria will then be scheduled for the baseline visit.

Participants will be reimbursed on an accelerated schedule with \$100 for their first visit and an increase in payments by \$25 for each subsequent visit, ending with a \$250 payment for the last post-partum visit. Participants will receive incentives in between visits including water bottles, tote bags, newborn t-shirts, etc. They also will be reimbursed with \$10 to cover travel costs for each visit.

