Power Calculations for Hypothesis 1. In this study with 108 participants in the supplement group and 54 in the placebo group, there will be >90% power to detect a difference in stress levels, at any particular visit, of the same magnitude as that observed in our preliminary study at 30 weeks (27.5+/-3.4 vs. 29.3+/-3.1), using a two-sided test at the 0.05 significance level. Additionally, with 162 participants, there will be 80% power to detect a correlation of 0.22 between changes in DHA levels in the blood versus changes in perceived stress. For the cortisol response to the TSST, there will be >95% power to detect a difference in AUCs at a given visit of the same magnitude as that found in our preliminary study at 30 weeks (-4.5+/-3.9 vs. -8.1+/-6.1; negative values indicating net decreases rather than increases), using a two-sided test at the 0.05 significance level.

Hypothesis 2. DHA supplementation during pregnancy will improve infant birth and developmental outcomes among African American women living in urban poverty.

Infants of mothers who receive DHA supplementation will have longer gestations, higher birth weights, more optimal neurodevelopmental outcomes as measured by the NBAS and Bayley Scales of Infant Development, and more optimal maternal reports of temperament in comparison to infants whose mothers did not receive DHA supplementation. We will use ANOVA (e.g. birth weight) or rmANOVA (e.g. NBAS) to test for significant differences between treatment groups. For categorical infant outcomes, such as pre-term birth or low Apgar scores, logistic regression will be employed. We will also test the association between level of DHA in blood at the last prenatal visit and/or change in DHA levels from baseline and infant outcomes using linear (e.g. birth weight or change in NBAS) or logistic (e.g. pre-term birth) regression.

Transformations of the continuous dependent measures will be performed to stabilize the variance across groups if needed.

Infants of mothers who received DHA supplements will demonstrate more modulated cortisol response to the NBAS and still-face paradigm, with a lower peak response and a steeper slope from peak to recovery, in comparison to infants whose mothers did not receive DHA supplementation. Analyses will be performed as described for Hypothesis 1.

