 Y_i is an outcome for infant i, g is a link function (e.g. logistic or identity), M_i is a maternal stress measure at the final prenatal visit for the mother of infant i, T_i is treatment group (e.g. 0=placebo vs. 1=active; average DHA level in the blood across prenatal visits), and Z_i is a vector of additional covariates such as infant gender, mothers' postpartum stress, depression, or anxiety. The change in ω due to adding maternal stress to the model provides an estimate of the proportion of the treatment effect due to this factor; if ω is still significant but the magnitude is reduced, this would provide evidence for partial mediation. For infant outcomes collected at multiple visits, the initial approach will be to use data from the last visit, but longitudinal approaches may be considered depending on the results from the initial analyses. To provide greater power for detecting such effects, bootstrapped confidence intervals will be examined. Since multiple measures of maternal stress will be collected, the model may be extended to permit multiple mediators.

Power Calculations for Hypothesis 3. Based on simulation results presented in Fritz et al. and the SAS program provided at http://ripl.faculty.asu.edu/wp-content/uploads/2013/02/baronkenny3.txt, 162 subjects will provide sufficient power (>80%) to detect the following effects based on Cohen's criteria. As shown in Figure 6 and Table 2, the study with 162 subjects will be sufficiently powered (>80%) to detect medium effects for the α and β paths and small effects for the direct effect (scenario 1), or small-medium effects for the α and β paths and medium effects for the direct effect (scenario 2), which is plausible based on the effects found in the preliminary study.

Table 2: Overview of power for mediation hypothesis

	α path	β path	Direct effect	
scenario 1	medium	medium	small	
scenario 2	small-medium	small-medium	medium	

Missing data. Missing data is not expected to be a major issue based on retention rates from the preliminary study. The last observation carried forward (LOCF) approach for missing data will be employed. Sensitivity analyses using complete-cases only will also be performed and the results using the two approaches compared. Related to this, treatment non-compliers will be included in the primary analysis based on the intent-to-treat (ITT) principle.

Timeline for participant visits

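### The plan lets women be excluded for medical complications that arise after randomisation, with no rule that keeps their birth data in the analysis

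*Combined protocol and SAP*

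**What the plan says.** The Participants section (under APPROACH) lists known medical complications among the exclusion criteria. It then adds a separate provision: "Participants may be excluded if medical complications arise after enrollment". The sentence after it reads "Neonates with significant medical complications will be maintained in the study". The same section assigns women at random to "omega-3 nutritional supplement (n = 112) or a corn and soybean oil placebo (n = 56) beginning at enrollment".

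The current plan does not define medical complications. The only examples are in the pilot's entry criteria, under Preliminary support for hypotheses: "Exclusion criteria were medical complications (e.g., gestational diabetes, pre-eclampsia". The plan does not say who decides on an exclusion, or whether the woman leaves the capsules, the visits, or the dataset.

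Hypothesis 2 states that "Infants of mothers who receive DHA supplementation will have longer gestations, higher birth weights", and adds: "For categorical infant outcomes, such as pre-term birth or low Apgar scores, logistic regression will be employed". Under Infant outcomes (Methods), birth outcomes are to be taken from the medical record.

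The Missing data paragraph says "The last observation carried forward (LOCF) approach for missing data will be employed", with a complete-case sensitivity analysis, and that "treatment non-compliers will be included in the primary analysis based on the intent-to-treat (ITT) principle".

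**The concern.** A complication that arises once supplementation has begun is a post-randomisation event. The plan's rationale gives reason to think that it bears on the birth outcomes. The Significance section lists obstetric complications beside shorter gestation and smaller infants as correlates of maternal stress. The Innovation section says that poor urban African American women, the population of this trial, are especially likely to have pregnancy complications. The hypothesised mechanism has maternal stress affecting the pregnancy, and the supplement is meant to reduce stress.

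Selecting on such an event gives up the protection of randomisation for the birth comparison. If the supplement changes the complication rate, unequal numbers of poor-outcome pregnancies leave the two arms. If it does not, the analysis still loses some of the events it was set up to count. The mediation analysis (Hypothesis 3) needs an infant outcome for each mother and would run on the same selected group. Because the provision is discretionary and undefined, a reader of the results could not reconstruct who was removed or why.

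**Working it through.** **1. Do the other rules keep an excluded woman in the birth analysis?**
- The intention-to-treat sentence covers women who do not take their capsules. It says nothing about women excluded by the investigators.
- Carrying forward needs an earlier value. Gestational age, birth weight and preterm status occur once and have none.
- The neonate sentence keeps infants with complications. It does not say that the infant of an excluded mother is kept.

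None of the three retains her birth data.

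**2. The plan's own birth-weight figure.** Inputs from Power Calculations for Hypothesis 2: 3174 ± 480 g against 2889 ± 549 g, 108 and 54 women, two-sided 0.05, stated power approximately 90%.
- Difference = 3174 − 2889 = 285 g.
- Standard error = √(480²/108 + 549²/54) = √(2133.3 + 5581.5) = 87.8 g. Ratio = 285/87.8 = 3.24.
- Power from the noncentral t with unequal variances: 89.5%. With a common SD of √[(480² + 549²)/2] = 515.7 g: 90.9%.

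The stated figure reproduces. It assumes 108 and 54 women analysed with no selective removal.

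**3. Preterm birth, equal share removed in both arms.** Pilot rates: 13% on supplement, 22% on placebo. Expected events at 108/54: 108 × 0.13 + 54 × 0.22 = 14.0 + 11.9 = 25.9. Suppose a share f of preterm births is excluded in each arm and nobody else is. The documents do not give f. The rate left is p(1 − f)/(1 − pf). The odds left are p(1 − f)/(1 − p), so (1 − f) cancels in the odds ratio: (0.13/0.87)/(0.22/0.78) = 0.53.

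| f (assumed) | Supplement | Placebo | Risk difference (points) | Odds ratio | Events lost | Power |
|---|---|---|---|---|---|---|
| 0 | 13.0% | 22.0% | 9.0 | 0.53 | 0 | 32% |
| 25% | 10.1% | 17.5% | 7.4 | 0.53 | 6.5 | 27% |
| 50% | 7.0% | 12.4% | 5.4 | 0.53 | 13.0 | 21% |
| 75% | 3.6% | 6.6% | 3.0 | 0.53 | 19.4 | 15% |

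Power is for a two-proportion test at two-sided 0.05 (normal approximation). The plan makes no power claim for preterm birth.

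**4. Preterm birth, unequal shares.** With shares f₁ (supplement) and f₀ (placebo), the odds ratio is multiplied by (1 − f₁)/(1 − f₀). For illustration, f₁ = 25% and f₀ = 50% give 0.53 × 0.75/0.50 = 0.79. Reversing them gives 0.53 × 0.50/0.75 = 0.35. The bias can go either way.

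**5. Birth weight.** Assume that a share c of pregnancies has complications, with babies D grams lighter, and that 285 g is the difference among all randomised women. Excluding all complicated pregnancies raises an arm's mean by cD, so the difference becomes 285 − (c₀ − c₁)D, where c₀ is placebo and c₁ is supplement. If only a share f of them is excluded, the arm's mean rises by D[c − c(1 − f)/(1 − cf)]. SDs are held at 480 and 549 g, and power uses unequal variances.

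| c₀, c₁ (assumed) | D (assumed) | Excluded | Difference | Power |
|---|---|---|---|---|
| 20%, 10% | 300 to 600 g | half | 272.5 to 260 g | 83% to 80% |
| 20%, 10% | 300 to 600 g | all | 255 to 225 g | 74% to 63% |
| 10%, 10% | 300 to 600 g | half | 285 g | 88% |
| 10%, 10% | 300 to 600 g | all | 285 g | 86% |

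If the rates were reversed (10% placebo, 20% supplement), excluding all would widen the difference to 315 to 345 g.

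**6. With everyone retained.** At 112/56 the power for 285 g is 90.5% with unequal variances, or 93.0% with the weighted pooled SD.

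**The case against.** The best defence is that the sentence sits under Participants, not under analysis, and is permissive. It may mean only that a woman can be taken off capsules or procedures. Neonates with complications are expressly kept, so a poor birth outcome is not in itself a ground for removal. Allocation is blinded, which limits deliberate selection. The four pilot withdrawals among 64 women were for miscarriage, mood changes, headaches and upset stomach; none was attributed to gestational diabetes or pre-eclampsia.

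Much of this stands. The ambiguity is real, and it is why the point is that the rule can remove women, not that it will. The pilot is weak reassurance, because the documents do not say whether it had the same rule. Blinding does not prevent bias when complication rates differ by arm.

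A reader might also draw three stronger conclusions that the documents do not support:
- That the rule breaks an explicit intention-to-treat rule. There is no statement that all randomised women are analysed. The inconsistency is with the principle invoked. Nor does the neonate sentence contradict the rule, since it concerns infants, not mothers.
- That exclusion shrinks the treatment contrast whatever the complication rates. With an equal share of preterm births removed, the odds ratio, which is what the planned logistic regression estimates, does not move. With equal complication rates and deficits, the 285 g difference stays.
- That half or more of the preterm births would be lost. No exclusion rate is given, and the shares above are assumptions.

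The link from treatment to complications is inferred too: Hypothesis 1 measures maternal health by perceived stress, inflammatory markers and stress reactivity, not by obstetric complications.

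**Conclusion.** The concern holds in this form. The plan permits an undefined, discretionary exclusion after randomisation, on an event that treatment may affect and that is plausibly related to the Hypothesis 2 outcomes. Nothing in the plan keeps the birth data of the women concerned. This is inconsistent with the intention-to-treat principle that the plan invokes.

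The documents determine neither the size nor the direction of any bias. With equal exclusion in both arms, the cost is events, precision and an estimate for a selected population: the risk difference shrinks, and the odds ratio stays at about 0.53. Bias in the planned comparison needs exclusion that differs by arm. Under assumed complication rates of 20% on placebo and 10% on supplement, and deficits of 300 to 600 g, the 285 g contrast would fall to between 272.5 and 225 g, with power of 83% to 63%. Reversed rates would inflate it. These figures also assume unchanged SDs, and that the pilot's 285 g describes all randomised women, which the documents do not establish.

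The point should be settled before enrolment, because data not collected from excluded women may not be recoverable later.

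**What to change.** Keep known medical complications as an eligibility criterion applied before randomisation. Replace the later sentence with a rule on data: a complication arising after randomisation does not remove a woman's or her infant's data from the study or from the intention-to-treat analysis. Then state that:
- birth outcomes will be obtained from the medical record for every randomised woman, where consent permits;
- all women will be analysed in the arm to which they were randomised;
- complications and any discontinuations will be reported by arm.

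Whether a woman continues capsules, the stress test or visits remains a separate clinical decision, which this change does not alter.

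The cost is a few sentences. The medical record is already the source of the birth outcomes, so no extra visit is needed. On the pilot figures, analysing all 168 women keeps birth-weight power at 90.5% or more. The small downside is somewhat more variable outcomes and some missed laboratory sessions among affected women.
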